## Methods

### Design and participants

#### *Domain*

Adult elderly patients scheduled for a non-cardiac surgical procedure with a moderate to high surgical risk that have a low blood pressure (IOH) during the procedure.

#### *Determinant*

A decision support system using two different types of notifications for IOH (for more detailed information see paragraph 'Decision support elements').

#### *Outcome*

Postoperative Acute Kidney Injury (AKI, see 'End points').

#### *Study design*

[figure not shown]
A single center, interrupted time series study with a nested cluster-randomized trial, randomized at the level of the anesthesia provider (see Figure 1). The study will be performed at Vanderbilt University Medical Center (VUMC). The study will use a 36-month historic cohort of procedures (retrospective data) from the baseline 'off' period, further referred to as the prein-

tervention period. Subsequently, the decision support system is implemented and its effects are recorded during the intervention period using routine clinical data. The decision support system consists of four interventional elements (see paragraph 'Decision support elements'), of which two are aimed at the attending anesthesiologist and two are aimed at the in-room anesthesia provider (the anesthesiology resident, the certified or student nurse anesthetists (CRNA or SRNA)).

The intervention period starts with the nested cluster-randomized trial. At the start of the intervention period, the attending anesthesiologists will be randomized to either of the two elements aimed at the attending. One month later, the in-room providers will be randomized to either of the elements that are aimed at them. The randomization status of the attending anesthesiologists will be maintained. After the third month, all elements will be activated for all users within that user group. This ends the period of the nested cluster-randomized trial. After the fourth month, an add-on for one of the decision support elements will be implemented. The exact nature of this add-on modification is discussed in the section 'Decision support elements'. The entire implementation phase will thus be completed in five months.

The study will then continue to monitor the incidence of the primary end point to reach the estimated sample size. The primary outcome is a routinely collected outcome variable, which enables us to: 1) use a historic cohort as a baseline 'off' period; 2) study the CDSS implementation in a pragmatic setting; and 3) conduct the study in a more cost-effective way. The total intervention period will be 9 months for the VUMC (Figure 1).

Figure 1 - Study design

### Study population

All adult inpatients, 60 years and older, scheduled for a non-cardiac surgical procedure under general or central neuraxial anesthesia at the Vanderbilt University Medical Center (VUMC).

### Exclusion criteria

Procedures where only a peripheral nerve blockade is used will be excluded, i.e. patients who did not receive either general anesthesia or central neuraxial blockade. Patients with preexisting end-stage renal disease will be excluded, operationalized as excluding all patients with a pre-operative need for dialysis. The following procedures will also be excluded: renal surgery, cardiac surgery, organ transplantation, ophthalmic surgery, endoscopic gastrointestinal procedures, and (interventional) radiologic procedures. Additionally, small non-invasive or minimally-invasive procedures will also be excluded.

### *Randomization during the nested cluster-randomized trial*

Each attending anesthesiologist and in-room provider will be randomized to either of the two interventions that is aimed at their user group. The randomization will occur at the start of the nested cluster-randomized trial period or at the time she/he enters the study within that period. Randomization at the provider level rather than at the patient level aims to prevent contamination and therefore dilution of the implementation effect. Randomization of the attending anesthesiologists will be stratified for the particular anesthesia expertise groups, e.g. vascular surgery anesthesia and neuroanesthesia. In-room providers will also be randomized per participating center, but stratified for being a resident, a CRNA or a SRNA. Randomization of CRNAs will be stratified on the OR-locations within their center where they mostly work. Stratified randomization will be performed using a block size of four.

### *Patients at risk of IOH*

The hypothesis of this study is that prevention of prolonged low blood pressures during anesthesia will reduce the incidence of organ injury, i.e. AKI and myocardial injury. The domain of this study therefore includes patients at risk of IOH. Identification of patients at risk of IOH is not straightforward. In this section we will discuss why identification of patients at risk of IOH is not straightforward and how this complicates the design of this study as compared to a regular randomized trial.

In a classical drug-RCT, you know that everyone in the index group will get the intervention, although you are not sure for which individuals the intervention will work. A more complex intervention often aims to improve patient outcome by implementing an intervention that is targeted to affect behavior and decision making of either healthcare workers or patients. For example, a weight loss program aims to reduce obesity in individuals. The mechanism through which the program achieves weight loss may not have the same effect in all individuals, similar to our drug trial. On top of that, an additional uncertainty is introduced, because the intervention will also depend on the compliance of the individual to the program.

When a complex intervention aims to prevent a particular condition – as in this case of IOH decision support – there is an additional complicating factor besides the two previously men-

tioned factors of uncertainty. When the condition can be completely prevented, the study population becomes difficult to identify. In our study, the decision support can only prevent AKI in patients that would otherwise have had IOH. Thus we should analyze only patients that would have had IOH, not patients that would never have IOH. Since we may not know which patients would have suffered from IOH in the intervention group, there is no simple comparison. Alternatively, we could compare the rates in all patients of both study groups – thus both those that would have had and would not have had IOH. However, as anesthesiologists already aim to prevent low blood pressures, patients with IOH according to our definitions will be relatively rare. Analyzing all patients would thus greatly dilute the effect on AKI and myocardial injury.

A more efficient way would be to compare patients that would be *at risk of IOH* rather than patients that would *definitely have had IOH*. A good example is comparing patients with different predicted risks when a prediction model is implemented to prevent postoperative nausea and vomiting. For IOH there is unfortunately no prediction model available. However, when IOH is prevented from occurring because of the implemented decision support, it is likely that they will have a low blood pressure that is just above the threshold. Patients that have a blood pressure below a higher threshold will thus be at risk of a blood pressure below a lower threshold, if it weren't for the intervention by the anesthesia providers. The next crucial step would be to select that higher threshold. Selecting too high a threshold will dilute the effect, whereas too low a threshold and patients may drop out because they are prevented from reaching that threshold. Although one cannot be sure what would be the best threshold in advance, it seems reasonable that a mean arterial pressure (MAP) below 65 mmHg would be a reasonable indication of MAP below either 60 mmHg or 55 mmHg.

## Interventions

The interventions in this study consist of a) the decision support elements; and b) general education.

### *Decision support elements*

The decision support system consists of four elements that aim to notify anesthesia providers of

the risks of organ injury due to organ ischemia when a patient suffers from IOH. The four elements will be implemented during different stages of the nested cluster-randomized trial period. At the end of the trial period all elements will be simultaneously activated (Figure 1).

The decision support system will be custom designed. The VUMC will implement two elements that provide near real-time notifications into GasChart, its anesthesia information management system (AIMS). The two other interventions consist of feedback emails, which be implemented into the email notification system of the Perioperative Data Warehouse (PDW).

One element of each decision support type will be available for each user group. In other words, a near real-time notification system and a feedback email system will be available for the attending anesthesiologists as well as for the in-room providers. During the cluster-randomized trial period, the near real-time elements will only be activated for a specific case when the anesthesia providers were randomized to near real-time decision support within their user group, as registered in the anesthesia information management system.

#### *IOH thresholds associated with organ injury*

The thresholds that will trigger decision support intervention are derived from recent literature. The studies were selected based on the results of a systematic review. For AKI, myocardial injury and mortality the two highest ranked studies for that end point were selected. For MAPs below 60, 55 and 50 mmHg and dependent on the duration of hypotension, the results of each study were classified into three risk groups (mild, moderate, high) based on the reported odds ratios or risk ratios. For each end point, the highest risk category for a particular MAP and duration was considered the definitive risk category for that end point. The overall risk of organ injury for a particular MAP and total duration was then considered to be the highest of risks of any of the end points. Risk thresholds for odds ratios and risk ratios were chosen by the investigators so that there was a clinically reasonable incremental increase in risk with lower MAPs and longer durations. The exact classification is shown in Tables 1 and 2.

Table 1 - Risk classification based on the odds ratios as reported in literature

MAP	min	AKI (odds ratios)		Myocardial injury (risk ratios / odds ratios)			30 day Mortality (odds ratios)	
		Sun et al.	Walsh et al.	Van Waes et al.†	Pipanmekaporn et al.†	Walsh et al.	Monk et al.	Mascha et al.
<60	≥1	1.1*		1.1*			1.1*	1.0‡
	>5	1.1*		1.1*			1.1*	1.1‡
	>10	1.8		1.5			1.1*	1.1
	>20	1.7*		1.5	2.6		1.1*	1.2
<55	≥1	1.4*	1.2	1.1*		1.3	1.1*	1.1‡
	>5	1.5*	1.2	1.1*		1.5	1.1*	1.1‡
	>10	2.3	1.3	1.5		1.8	1.1*	1.1
	>20	3.5	1.5	1.5	2.6	1.8	1.1*	1.3
<50	≥1	1.4*	1.2	1.3		1.3	1.2*	1.1‡
	>5	1.5*	1.2	2.0		1.5	2.4	1.1‡
	>10	2.3	1.3	2.0		1.8	2.4	1.2
	>20	3.5	1.5	2.4	2.6	1.8	2.4	1.5

\* = not significant; † = the numbers in this column are risk ratios; ‡ = estimated from OR per 10 minutes

yellow = mild risk; light orange = moderate risk; dark orange = high risk

risks from higher MAP groups carry over to lower groups if that particular threshold was not reported in the study

Table 2 - Classification of depth and duration of IOH

MAP	total minutes	overall organ injury*	acute kidney injury	myocardial injury	30 day mortality
<60	≥1	mild risk	mild risk	mild risk	mild risk
	>5	mild risk	mild risk	mild risk	mild risk
	>10	moderate risk	moderate risk	moderate risk	mild risk
	>20	high risk	moderate risk	high risk	mild risk
<55	≥1	mild risk	mild risk	mild risk	mild risk
	>5	moderate risk	moderate risk	moderate risk	mild risk
	>10	high risk	high risk	moderate risk	mild risk
	>20	high risk	high risk	high risk	mild risk
<50	≥1	moderate risk	mild risk	moderate risk	moderate risk
	>5	high risk	moderate risk	high risk	high risk
	>10	high risk	high risk	high risk	high risk
	>20	high risk	high risk	high risk	high risk

\* the risk of overall organ injury (2nd column) is determined by the highest risk classification of the individual risks (3rd to 5th columns). The red bar represents the risks of the current patient.

### *Postoperative feedback emails*

The first two elements consist of the same email notification aimed at different anesthesia providers: the attending anesthesiologists or the in-room providers. The anesthesia providers will be notified within 24 hours after the end of a case, when the patient had an episode of IOH that is associated with an increased risk of organ injury due to organ ischemia. The feedback email will primarily report the risk of AKI at VUMC. In addition, the feedback emails will include a link to a more detailed description of all organ risks (see Table 2 and the Example for the Feedback emails). Moreover, at the end of each week, the anesthesia providers will receive an email that reports which of their patients suffered from postoperative AKI or myocardial injury that week (such a report is already a part of clinical routine at VUMC). As the follow-up for AKI is seven days, the update may contain patients that had their procedure during the previous 14 days.

### *Near real-time notifications*

[figure not shown]
The two near real-time decision support elements will notify the anesthesia provider of a blood pressure drop below one of the IOH thresholds. The near real-time notification for the attending anesthesiologist will be provided through the paging systems (example text: “MAP<50 for 10min, high AKI risk”), whereas the in-room providers receive their notification through the AIMS of the hospital (see attached Example for the AIMS IOH notification).

### *Triggers of near real-time notifications*

The near real-time notifications systems will be triggered by a MAP below 60 mmHg (Figure 2). The decision support system will then provide a notification of the AKI risk at VUMC. Depending on how much time the MAP of an individual patient was below a particular threshold, the notification will display the risk of organ ischemia for that patient (mild, moderate or high, see Table 2). An example in time is shown in Figure 2 – examples 1 and 2.

The near real-time notifications for the in-room providers will be continuously displayed within the AIMS. The near real-time notifications for the anesthesiologists will be sent to their pagers. The pager notifications will repeat with a 10-minute interval. Within a single episode of IOH there will be a maximum of four notifications the paging system (Figure 2 – example 3). An episode of IOH is defined as the time that a patient’s MAP drops below 60 mmHg and the first time it reaches a MAP of 60 or higher. When blood pressure has not returned to normal after the four notifications – i.e. after 40 minutes – it is assumed that there is a reason for not increasing the blood pressure. In that instance either the MAP is considered to be appropriate for that patient or the interventions are not sufficiently effective. This prevents anesthesiologists to keep getting notifications throughout the procedure. Even when a new duration threshold is reached, the system will not provide a new notification if four notifications within that episode have already occurred. However, when the blood pressure normalizes for more than 20 minutes, a subsequent IOH episode will again provide notifications to the low MAP. Any risk that is presented, is based on all the previous low MAP values and durations that occurred during the case (Figure 2 – example 4).

Figure 2 - Triggers of near real-time notifications

### *General education*

All attending anesthesiologists and in-room providers will be informed at the start of the nested trial period – or when they enter the study at a later time – of the study’s purposes and how the decision support will work. The information will be provided by email as well as during scheduled educational sessions for each provider group. Further educational sessions will be scheduled when required.

## End points

### *The primary end points*

The primary end point for the VUMC will be AKI stage I or greater within the first seven postoperative days of surgery. The definition of AKI stage I according to KDIGO (Kidney Disease: Improving Global Outcomes) will be used: an absolute increase in serum creatinine of 0.3 mg/dL or more ( $\geq 26.4 \mu\text{mol/L}$ ) from baseline within 48 hours or a percentage increase in serum creatinine to 150% or more from baseline within 7 days. Because of a low availability of information on urine output, this criterion will not be used to diagnose AKI. The baseline serum creatinine value is the last known preoperative value which was recorded within six months prior to the surgical procedure. Preoperative and postoperative creatinine values will be derived from blood samples that are part of routine clinical care. This may be a primary lab request for creatinine or a secondary analysis of blood samples that are otherwise available. No additional blood samples will be drawn for the purpose of this study to determine postoperative AKI at the VUMC.

### *Secondary end points: patient level*

- 30-day mortality
  - combination of in-hospital mortality and ‘alive-index’ (which checks for visits to the hospital in the electronic healthcare record as indication of being alive)
- In-hospital mortality

- length of hospital stay
- ICU admission
- length of ICU stay (if any)
- readmissions
- AKI stage 2 or greater (to a 200% or more increase in baseline creatinine value)
- postoperative rise in creatinine levels

*Secondary end points: process level*

- the incidence of IOH
- the depth and duration of IOH
- estimated blood loss
- time to discharge readiness at the PACU

*Secondary end points: behavior level*

- anesthetic/analgesic drug use
  - average concentrations of inhalational anesthesia during MAP < 65 mmHg episodes
- average use of the following blood pressure interventions during the entire case
  - vasopressor use
  - inotropic use
  - intravenous fluid administration
  - blood products administration
- time to first blood pressure intervention after MAP drops below
  - 65 mmHg
  - 60 mmHg
  - 55 mmHg
  - 50 mmHg

## Data collection

Primary and secondary patient end point data are routine clinical data that will be collected from the medical records of the hospital electronic patient record keeping system, which are already linked to the existing perioperative data warehouses. Behavioral end point data will be extracted from the perioperative data warehouse (PDW) of the VUMC. Collection of end point data will automatically be performed, guaranteeing an end point assessment that is independent of the randomization status of providers and procedures.

## Data safety monitoring

The principal investigator (PI) will be responsible for data safety and monitoring within the VUMC. Quality control will include regular data verification and protocol compliance checks. Protocol adherence at the VUMC will be monitored by the PI throughout the study. Events determined by the PI to be unanticipated problems involving risks to subjects will be reported by the PI to the VUMC IRB within 10 working days of the Investigator's knowledge of the problem.

All study staff members will be informed about any unanticipated problems involving risks to participants or others associated with the research (such as a breach of confidentiality). If any protocol changes are needed, the PI will submit an amendment request to the VUMC IRB. Protocol changes will not be implemented prior to IRB approval unless necessary to eliminate apparent immediate hazards to the research subjects. In such a case, the IRB will be promptly informed of the change following implementation (within 10 working days).

The PI will permit inspection of all study-related records by the IRB and responsible governmental agencies. Within legal and regulatory restrictions and institutional and ethical considerations, the PI will permit the review of source documents in order to verify data in the study records. The PI will provide oversight during the course of the study. All study data will be handled confidentially.

## Sample size calculation

Sample size calculations were performed in *R* software. As mentioned earlier, we calculated

sample sizes for each of the participating centers, because they will use a different primary end point. The required sample sizes were calculated for both primary end points. Sample size calculations assumed a power of 0.8 and a Type 1 error rate (alpha) of 0.05. Based on earlier experiences with decision support intervention studies, we assumed there would be no clustering of primary end point data at the provider level.

Using historic data from the VUMC, the incidence of any MAP below 65 mmHg were estimated at 60% for patients that meet the inclusion criteria. Within this study population – any MAP < 65 mmHg – the incidence of AKI stage I was 9.8%. We derived the assumed treatment effect from the odds ratio (OR) reported by Sun et al. They reported an odds ratio of 1.8 (originally 1.84) for postoperative AKI in patients that had a MAP below 60 mmHg for 10 minutes or more. Thus the possible treatment effect within patients having a MAP < 60 mmHg for 10 minutes or more is then an OR of 0.56 (the inverse of 1.8). Within the study population (any MAP < 65 mmHg), the incidence of MAP < 60 mmHg for 10 minutes was 43%. Applying the OR 0.56 to an incidence of 43% resulted in an overall OR of 0.78 within the study population. The intervention phase (9 months) is four times shorter than the preintervention phase (36 months), resulting in a fraction of 0.20 of the total study period (9 divided by 45). As the intervention might not be as efficient during the nested cluster-randomized trial period, we used only half of the three months trial period, reducing the fraction of the intervention phase to 0.17. Additionally, we included a 20% margin of error to the sample size of the intervention period. The resulting calculated sample size is 2,005 procedures for the intervention phase and 8,019 procedures for the preintervention phase (Table 3). With an average of 275 procedures per month meeting the inclusion criteria, the calculated sample size is feasible within the specified time periods.

The calculations above assume that all episodes of prolonged hypotension will be treated during the intervention phase, which is unlikely. However, it also assumes that preventing shorter amounts of IOH (< 10 minutes) does not have any effect on patient outcome (an OR of 1.0), which is also unlikely. Consequently, the second assumption may compensate for the first assumption. As a sensitivity analysis we calculated the sample sizes for different combination of a different treatment percentage and an OR > 1.0 for patients with a MAP < 60 for 1-10 minutes

(Table 3). This sensitivity analysis shows that the calculated sample sizes indeed include an error margin for the assumption on the IOH treatment percentages.

Table 3 - Sample size calculation with sensitivity analyses

	Sample sizes calculated			
	Center	n	intervention phase	preintervention phase
sample size including 20% error margin	AKI (VUMC)	10024	2005	8019
sample size without 20% error margin	AKI (VUMC)	9690	1671	8019
80% of hypotension treated OR 1.1 MAP < 60 for 1-10 min.	AKI (VUMC)	11432	1971	9461
70% of hypotension treated OR 1.2 MAP < 60 for 1-10 min.	AKI (VUMC)	11910	2054	9857

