## Statistical analysis

### *Primary end points*

The analysis of the primary end point will be performed under the intention-to-treat principle, and only include patients that have had a MAP below 65 mmHg for at least one minute during the procedure. As the study is an interrupted time series design, segmented regression models will be used for both primary end points. The different study groups within the nested cluster-randomized trial will not be separately analyzed because of a too small sample size.

A two-sided alpha of 0.05 will be considered to be statistically significant. Continuous variables will be visually assessed for a normal distribution using histograms and QQ-plots. In descriptive statistics, parametric variables will be expressed as means with standard deviations, nonparametric variables will be expressed as medians with interquartile ranges, and discrete variables will be expressed as numbers with percentages. Missing data will be multiply imputed

using a regression approach. Before multivariable modelling, all continuous variables will be tested for nonlinearity using restricted cubic splines.

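### The stated power of 0.8 belongs to a before-after comparison with no time term; if the primary segmented regression estimates a secular trend, its power for an immediate constant effect is about 53–69%

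*Combined protocol and SAP*

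**What the plan says.** 'Sample size calculation' states: "Sample size calculations assumed a power of 0.8 and a Type 1 error rate (alpha) of 0.05". Its inputs are an AKI rate of 9.8% in procedures with any MAP below 65 mmHg, an effect of 0.78, and the share of study time in each phase. The effect is described thus: "Applying the OR 0.56 to an incidence of 43% resulted in an overall OR of 0.78 within the study population". Half of the three-month nested trial is discounted, so the intervention phase counts as 7.5 months against 36. Table 3 gives 8,019 + 1,671 in the row "sample size without 20% error margin", and 8,019 + 2,005 with the margin. Its two sensitivity rows vary only the percentage of hypotension treated and the odds ratio for short hypotension. On accrual: "With an average of 275 procedures per month meeting the inclusion criteria, the calculated sample size is feasible within the specified time periods".

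Under 'Statistical analysis', 'Primary end points': "As the study is an interrupted time series design, segmented regression models will be used for both primary end points". The same section adds: "A two-sided alpha of 0.05 will be considered to be statistically significant".

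'Study design' sets the time axis: "The study will use a 36-month historic cohort of procedures (retrospective data"), followed by 9 intervention months. Attendings are randomised at the start and in-room providers one month later. Then: "After the third month, all elements will be activated for all users within that user group". An add-on follows after the fourth month. No section says which of these dates is the breakpoint, which time terms enter the model, or which coefficient is the primary test.

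**The concern.** The power was calculated for one test and the plan commits to another. A before-after comparison of two rates asks only whether the phases differ. A segmented regression with a trend asks whether AKI departed from the line already being followed. Study phase and calendar time are strongly correlated here, because all 9 intervention months come last, so estimating the trend takes information away from the step.

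Two things are at stake. First, a reader will take 0.8 as the power of the primary test, and a null result would be read as stronger evidence of no effect than it is. Second, because the contrast is not named, the choice between a model that adjusts for trend at the cost of power and one that keeps power but is exposed to drift could be made after the data are seen.

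**Working it through.** **Inputs.** From the plan: two-sided alpha 0.05, power 0.80, baseline p₁ = 0.098, effect 0.78 (0.56^0.43 = 0.779), ratio k = 7.5/36 = 0.2083, phases of 36 and 9 months, 275 procedures per month, 60% of eligible patients with MAP below 65 mmHg. Assumed here because the plan is silent: monthly cells, even accrual, linear trend on the logit scale, no true trend (except in step 6), an immediate constant effect, and no autocorrelation, clustering or covariates.

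**1. Reproduce the stated size.** With p̄ = (p₁ + k·p₂)/(1 + k),

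n₁ = [1.960·√(p̄(1−p̄)(1+1/k)) + 0.8416·√(p₁(1−p₁) + p₂(1−p₂)/k)]² / (p₁−p₂)², and n₂ = k·n₁.

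- 0.78 as a risk ratio: p₂ = 0.098 × 0.78 = 0.0764. n₁ = (1.3794 + 0.5501)² / 0.02156² = 8,009 and n₂ = 1,669. The plan has 8,019 and 1,671, and 1,671 × 1.2 = 2,005. This reproduces within 0.2%.
- 0.78 as an odds ratio: baseline odds 0.098/0.902 = 0.1086, so p₂ = 0.0847/1.0847 = 0.0781. n₁ = 9,486 and n₂ = 1,976. This does not reproduce.

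The formula contains no time term, so the 0.8 belongs to the two-rate comparison.

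**2. Power of that unadjusted comparison.** Two-proportion power with the risk ratio: 80.1% at 8,019 + 1,671 and 85.8% at 8,019 + 2,005. With the odds ratio: 72.7% and 79.3% (71.2% and 77.7% by a logistic Wald test).

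**3. Add a linear trend.** Model: logit P(AKI) = β₀ + β₁·post + β₂·time over 45 months. The SE of β₁ comes from the inverse of X′WX, with weights n·p(1−p) per month. Power ≈ Φ(|log OR|/SE − 1.960). At 8,019 + 2,005 with OR 0.78 (|log OR| = 0.2485):

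- level only: SE 0.0913, Φ(2.722 − 1.960) = 77.7%
- level and common trend: SE 0.1219, Φ(2.038 − 1.960) = 53.1%
- variance ratio: (0.1219/0.0913)² = 1.78. The approximation for equal information per month, 1/(1 − 3f(1−f)), gives 1.92 at f = 0.20.

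Risk ratio 0.78 corresponds to OR 0.762 at this baseline. All cases:

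| Procedures | Effect | Level only | Level + common trend |
|---|---|---|---|
| 8,019 + 2,005 | OR 0.78 | 77.7% | 53.1% |
| 8,019 + 2,005 | risk ratio 0.78 | 84.0% | 60.3% |
| 9,900 + 2,475 (275/month) | OR 0.78 | 85.6% | 61.9% |
| 9,900 + 2,475 (275/month) | risk ratio 0.78 | 90.7% | 69.4% |
| 5,940 + 1,485 (275 × 0.60 = 165/month) | OR 0.78 | 64.9% | 41.8% |
| 5,940 + 1,485 (275 × 0.60 = 165/month) | risk ratio 0.78 | 72.0% | 48.1% |

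The last pair applies if the 275 are counted before selecting MAP below 65 mmHg. Simulation (6,000 runs per scenario) of the first four common-trend cases gave 53.5%, 60.9%, 60.9% and 70.0%, and 4.8% under no effect.

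**4. What 80% would take with a common trend.** At 8,019 + 2,005 the detectable OR is about 0.71. Holding the effect fixed, about 12,760 + 3,190 (risk ratio, 1.6 times the plan) to 15,160 + 3,790 (odds ratio, 1.9 times).

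**5. Other contrasts and effect shapes.**

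- With a slope change also fitted, the level coefficient alone has about 27–30% (OR 0.78, 8,019 + 2,005), depending on where time is centred.
- If the effect grows linearly from zero and its average log odds ratio over the 9 months equals that of 0.78 (so it is about twice as large by the end), the month-9 contrast has 69% (OR, 8,019 + 2,005) up to 84% (risk ratio, 9,900 + 2,475).
- If only half the log-OR effect is present in the first three months, the common-trend step has about 38–51%.

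**6. Cost of leaving the trend out.** With no intervention effect, at 8,019 + 2,005, and AKI odds assumed to fall by 2%, 3% or 5% per year, a level-only test rejects in 7.3%, 10.3% or 20.1% of studies. The common-trend step stays at 5%.

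**The case against.** The strongest reply is that the plan never says a trend will be fitted. 'Additional analyses: specific clinical research questions' describes the preceding analyses as comparing end points between study periods, which is what the sample size models, and a level-only model would roughly meet or exceed 0.8 at the planned numbers. This stands to the extent that the shortfall is conditional. It does not rescue the plan: segmented regression is justified there by the interrupted time series design, and a level-only fit is just the before-after comparison.

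Other points also stand in part:

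- The low end of the range combines two issues. With 0.78 as a risk ratio, the effect that produced the stated size, the trend term alone gives 60–69%; the drop to 53% at 8,019 + 2,005 comes from taking the odds-ratio label at its word.
- An immediate constant effect is not what a staged rollout suggests. A half effect in the first three months lowers power further, whereas a growing effect tested at month 9 can do better.
- The 2–5% yearly drift is an illustration; the plan gives no such figure. It does foresee multivariable modelling, so case-mix drift might be partly adjusted.

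These limit how precisely the loss can be stated. None supplies a time term in the sample size or names the primary contrast.

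**Conclusion.** The concern holds. Three things follow from the documents without further assumption: the sample size has no time term, the primary contrast is not specified, and 0.78 reproduces the stated numbers only as a risk ratio although it is called an odds ratio. Taken at its label, 0.78 gives about 71–73% power at 8,019 + 1,671 even before any trend is considered.

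The size of the further loss is conditional. With a common linear trend and an immediate constant effect, power is 53–69% across the planned and the expected accrual. A true effect of the assumed size would then be missed in about 31–47% of such studies, not 20%. Other contrasts and effect shapes give figures from below this range to 84%, so no single percentage should be read as the power of this study. It should be fixed before analysis.

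**What to change.** In 'Statistical analysis', name the one segmented-regression contrast that is the primary test, with its time terms, its breakpoint and the handling of the rollout months.

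In 'Sample size calculation', replace 0.8 with the power and detectable effect of that contrast, from the sponsor's own calculation, and state whether 0.78 is an odds ratio or a risk ratio. It would help to say in the same place whether the 275 procedures per month are counted before or after selecting MAP below 65 mmHg. If 0.8 is kept, say that it applies only to an unadjusted before-after comparison of 8,019 + 1,671 with 0.78 as a risk ratio; with an odds ratio of 0.78 that comparison has about 71–73%, or 78–79% with 2,005 intervention procedures.

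State the trade-off openly: a trend term lowers power, while a level-only test keeps it but cannot separate the intervention from drift.

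The cost is protocol and SAP wording and one power calculation. The stated power becomes less favourable; no extra patients or data are needed.
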